7.4 Actual Time

The unknown and duplicate actual time will be managed as per

SOPs.

The plasma NCA analysis will be based on actual sampling times, except for predose samples, which will be reported as zero, regardless of time deviations provided that they are collected prior to dosing.

The individual plasma concentration-time profiles will be presented by dose level using actual sampling times whereas the mean plasma concentration-time profiles, and tables of summary statistics for concentration-time data will be presented using nominal sampling times.

Protocol No. INDV-2000-101

The actual times will be listed in the report.

7.5 NCA Analysis

The following configuration for the NCA analysis (with Phoenix[®] WinNonlin[®] version 8, or higher) will be used:

Data: Serial sampled data

Model/Dose options Type: Plasma (200 - 202)

Extravascular

AUC Calculation Method: Linear Up / Log Down (applicable for plasma only)

Lambda _Z (λ_z) calculation: Best fit method for λ_z Linear-Log regression

Reason for exclusion of AUC: In the case where less than 3 consecutive measurable plasma concentrations are observed, the AUC parameters will not be estimated.

The plasma PK parameters requiring λ_z will not be estimated, and will be presented as not calculated (NC), if at least one of the following criteria is not met:

- $R^2 > 80\%$
- The terminal phase consists of less than 3 data points or
- $%AUC_{extrap} < 20\%$

The following PK parameters will be calculated for INDV-2000 and M12:

 Table 3: Pharmacokinetic Parameters

Parameter	Definition
C _{max}	Maximum observed plasma concentration
C _{max} /D	Dose-normalized C _{max} (INDV-2000 only)
t _{max}	Time of maximum observed plasma concentration; if the maximum observed concentration is not unique, then the first maximum is used
AUC _{0-last}	Area under the concentration time curve from the time of last dosing to t_{last}
AUC _{0-last} /D	Dose-normalized AUC _{0-last} (INDV-2000 only)
AUC _{0-inf}	Area under the concentration time curve extrapolated to infinity, calculated as $AUC_{0-last} + C_{last}/\lambda_Z$, where C_{last} is the measured concentration at time t_{last}
AUC _{0-inf} /D	Dose-normalized AUC _{0-inf} (INDV-2000 only)
AUC _(t1-t2)	Area under the plasma concentration-time curve from t1 to t2 where t1 and t2 represents urine collection interval t1-t2 shorter than the

Parameter	Definition					
	scheduled interval of 0-T.					
	Note: This AUC will be estimated to support calculation of CLr over a truncated interval in the event a void is missed during a collection interval resulting in a shorter interval than the scheduled interval from 0-T; otherwise, it will not be estimated					
%AUC _{extrap}	$ \begin{array}{c} Extrapolated area (i.e. \ percentage \ of \ AUC_{0\text{-}inf} \ due \ to \ extrapolation \ from \\ t_{last} \ to \ infinity) \end{array} $					
t _{1/2}	Plasma terminal elimination half-life, calculated as $ln(2)/\lambda_Z$					
CL/F	Apparent plasma clearance, calculated as Dose/AUC _{0-inf} (INDV-2000 only)					
V _z /F	Apparent volume of distribution, calculated as Dose/ λ_Z * AUC _{0-inf} (INDV-2000 only)					
The following p PK listings only	lasma PK parameters will be used for PK calculation and presented in the					
t _{last}	Time of last measurable (positive) observed concentration					
R ²	Goodness of fit for the terminal elimination phase					
Number of Points	Number of data points in computing λ_Z					
λ_z	Apparent elimination rate constant, estimated by linear regression of the terminal linear portion of the log concentration versus time curve					
$\lambda_{z \; Upper}$	Upper limit on time for values included in the calculation of λ_z					
$\lambda_{z \; Lower}$	Lower limit on time for values included in the calculation of λ_z					

Protocol No. INDV-2000-101

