#### 2.2 Secondary

The secondary objectives of this study are to:

- Determine the maximum tolerated single dose of INDV-2000
- Characterize pharmacokinetics for single doses of INDV-2000
- Determine potential effects of a high-fat meal on drug absorption and exposure

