#### 3.2 Secondary

- Clinical safety assessments
  - o laboratory results
  - o electrocardiogram (ECG) findings
  - o vital sign measures
  - physical examination
- Plasma PK parameters of single doses of INDV-2000
  - $\circ$   $C_{max}$
  - $\circ$  Tmax (Time to reach maximum (peak) plasma concentration following drug administration)
  - o AUC₀-t, AUC₀-∞
  - o CL/F
  - $\circ$  Plasma terminal half-life (t1/2)

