## 8.10 Pharmacokinetic Assessments

## 8.10.1 Plasma Samples for Pharmacokinetic Analysis

Blood samples for PK analysis of INDV-2000 metabolite metabolite will be collected at the time points listed in Section 22.4, Appendix 4. Depending on PK results from the first dose levels, up to 2 additional samples may be added or the schedule of samples may be modified. Approximately 14 blood samples of 6 mL per sample for PK in total will be taken from any subject, however, it could be more if the subject experiences an SAE, or requires their
sample(s) retaken. The actual date and time of each sample collection will be documented. Samples will be collected into appropriate tubes as specified by the bioanalytical laboratory. Details of sample tubes, processing, storage and shipping procedures are provided in the Laboratory Manual.

Additional PK samples may be collected for subjects who experience a SAE. Samples should be collected as soon as the Investigator is made aware of the SAE and additional blood samples may be collected, after a period of time, to confirm resolution of the SAE.

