# 22.4 APPENDIX 4 – Pharmacokinetic Sampling Windows Part I

Day	Timepoint	Assessment	Window	
Day 1	pre-dose			
Day 1	0.5 hr post-dose			
Day 1	1 hr post-dose			
Day 1	2 hr post-dose			
Day 1	3 hr post-dose			
Day 1	4 hr post-dose			
Day 1	6 hr post-dose			
Day 1	8 hr post-dose			
Day 1	12 hr post-dose			
Day 2	24 hr post-dose			
Day 3	48 hr post-dose			
Day 4	72 hr post-dose			

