7.6 Pharmacokinetic Statistical Methodology

7.6.1 Summary Statistics

Summary statistics of the individual concentration data and derived parameters will be calculated with the built-in Phoenix[®] WinNonlin[®] platform and displayed with the same precision as received from the bioanalytical laboratory; additional details on precision rules are provided in Section7.7.

Descriptive statistics will be calculated for INDV-2000 and M12 plasma concentrations for each nominal time point and for all PK parameters,

Plasma Plasma individual concentrations and PK parameters obtained from the NCA will be summarized using the following summary statistics: N, minimum (min), arithmetic mean (mean), geometric mean (for main plasma PK parameters only), median, maximum (max), standard deviation (SD), CV%, and geometric CV% (for main plasma PK parameters only).

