10 INTERIM ANALYSES AND DATA SAFETY MONI

In Part I, there will be a review of safety data for the sentinel group in each cohort before proceeding to the next subject in the cohort. There will also be a review of the safety and PK data for each cohort before dose escalation. The safety data review will be conducted by the DRSC using stopping rules defined in Section 3.6.2.

PK parameter estimation for safety review will be performed using bioanalytical data applied with subject aliases in order to maintain the study blind. PK analysis will be performed using nominal time points. The preliminary PK results of INDV-2000 and M12 at the time of the safety review will be performed as outlined in Section 7, with the exception that nominal times will be used in the analysis instead of actual times. Mean concentration-time profiles as well as parameter summary tables of the key PK parameters (e.g. C_{max} , T_{max} , and AUCs) will be generated. PK data will not be part of the safety review.

No safety review will be performed for Part II.

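### The 20% extrapolation rule in SAP 7.5 drops long half-lives because they are long, so the planned t1/2 summary is biased low if typical t1/2 is about 24 h or more

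*SAP*

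**What the plan says.** Protocol 2.2 lists as a secondary objective "Characterize pharmacokinetics for single doses of INDV-2000". Protocol 3.2 names AUC0-inf, CL/F and "Plasma terminal half-life" among the secondary endpoints. In Protocol Appendix 4 the last plasma sample in Part I, and in each Part II period, is at "72 hr post-dose".

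SAP 7.5 states that parameters requiring the terminal slope "will not be estimated, and will be presented as not calculated (NC), if at least one of the following criteria is not met". Three criteria follow: R-squared above 80%, a condition on having 3 terminal points, and an extrapolated share of AUC below 20%. SAP Table 3 derives t1/2, AUC0-inf, CL/F and Vz/F from the slope, so all four become NC together.

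SAP 7.6.1 then says that "PK parameters obtained from the NCA will be summarized using the following summary statistics", with N among them. SAP 9.3 rules out imputation. The visible text has no rule to keep and flag such values, and no sensitivity summary that includes them. The slope itself, described as "Apparent elimination rate constant, estimated by linear regression of the terminal linear portion of the log concentration", appears in listings only.

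**The concern.** The extrapolated share of AUC rises with the half-life. A limit on that share therefore selects subjects by the quantity being estimated. A subject with a long half-life and a clean terminal slope is removed in the same way as one with a poor slope, although R-squared and the 3-point condition already screen poor slopes.

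The subjects left are a sample cut off from above. Their mean t1/2 is too short and its spread too small. Where clearance drives the half-life, AUC0-inf is too low and CL/F too high. If 72 h is measurable, the error runs the same way in every cohort, so more cohorts do not average it out. Protocol 1.4 says that human PK is not yet characterized, so these would be the first human values. SAP 10 applies the Section 7 methods, with nominal times, to the preliminary "parameter summary tables of the key PK parameters".

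**Working it through.** The documents give no figure to reproduce here, and no human half-life. Half-lives, CVs and noise below are assumptions.

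**Inputs from the documents.** Last sample 72 h (Protocol Appendix 4); extrapolation limit 20% (SAP 7.5); 6 active subjects per Part I cohort (Protocol 5.1).

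**Step 1: individual cut-off.** For mono-exponential decline the extrapolated share is 2^(-72/t1/2). It is 8.2% at 20 h, 12.5% at 24 h, 16.8% at 28 h and 25% at 36 h. Setting it to 20% gives t1/2 = 72 × ln 2 / ln 5 = 49.91 / 1.609 = **31.0 h**.

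If a fast first phase leaves the terminal phase with share f of total AUC, the cut-off is 72 × ln 2 / ln(f/0.20): 33.2 h for f = 0.9, 36.0 h for 0.8 and 45.4 h for 0.6.

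**Step 2: effect on the group summary.** Take t1/2 as lognormal with geometric mean m and s = sqrt(ln(1 + CV²)), which is 0.198 for CV 20% and 0.294 for CV 30%. With b = ln(31.0/m)/s, the share reported is Φ(b), and the ratio of the reported to the true geometric mean is exp(-s φ(b)/Φ(b)). For m = 24 h and CV 30%: b = 0.873, Φ = 0.809, φ = 0.273, ratio = exp(-0.294 × 0.273/0.809) = 0.906.

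| Typical t1/2 | Reported, CV 20% / 30% | t1/2 ratio, CV 20% / 30% |
|---|---|---|
| 16 h | 100% / 99% | 1.00 / 0.99 |
| 20 h | 99% / 93% | 0.99 / 0.96 |
| 24 h | 90% / 81% | 0.96 / 0.91 |
| 28 h | 70% / 64% | 0.91 / 0.84 |
| 36 h | 23% / 31% | 0.77 / 0.71 |

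**Step 3: simulated NCA.** One compartment, protocol sampling times, ka 1/h, linear-up/log-down AUC, best-fit slope, R-squared above 80%, 10% noise, variability in clearance, 72 h measurable, CV 20-30%.

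| Typical t1/2 | Reported | t1/2 low by | AUC0-inf low by |
|---|---|---|---|
| 24 h | 79-88% | 5-11% | 4-10% |
| 28 h | 62-66% | 11-18% | 10-17% |
| 36 h | 23-32% | 26-30% | 22-28% |

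CL/F is 5-11% high at 24 h and 11-20% high at 28 h. At 28 h a true t1/2 CV of 30% shows as 19%. Without the 20% limit, t1/2 and AUC0-inf are within about 1% of truth. If t1/2 varies only through volume, AUC0-inf bias is at most 2%, while t1/2 bias is unchanged.

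**Step 4: does bias matter beside sampling error?** At n = 6 the log-scale standard error of a geometric mean is s/√6, or 0.08 for CV 20% and 0.12 for CV 30%.

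- At 20 h, cohort-of-6 RMSE for t1/2 is no worse with the limit: 0.082 with it against 0.087 without (CV 20%, 10% noise), and 0.119 against 0.124 (CV 30%, 10% noise).
- At 24-36 h, with CV 20-30% and noise 10-20%, removing the limit lowers the error in all 12 settings tested. At 28 h, CV 30% and 10% noise it falls from 0.219 to 0.132.

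**Step 5: two-phase profiles.** In one simulated case (80/20 amplitudes, low LLOQ, CV 30%, typical terminal t1/2 25 h), 9% are excluded. The t1/2 summary is 11% low with the limit and 5% low without it, and AUC0-inf is 3% low with it. Here about half of the t1/2 bias comes from the slope fit.

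**The case against.** **Sampling can be extended.** Protocol 8.10.1 says that "up to 2 additional samples may be added or the schedule of samples may be modified" after the first dose levels. Samples at 96 and 120 h would move the cut-off to 120 × ln 2 / ln 5 = 51.7 h. In simulation (CV 30%, 10% noise) t1/2 is then only 2% low at 28 h and 8% low at 36 h. This stands as a real remedy, but it is optional, has no stated trigger, and leaves the SAP rule unchanged.

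**Withholding imprecise values is a legitimate choice.** Half-lives from heavily extrapolated profiles are less precise, and the PK analysis is descriptive with no power basis. That is fair, and it is why the fix keeps the filtered summary beside the full one.

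**The loss is visible.** N is printed, and lambda-z is listed, so t1/2 can be recovered by hand. Cmax and AUC0-last are unaffected. All true, but the planned summary tables stay uncorrected.

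**Text may be hidden.** SAP 7.2 and the food-effect part of 7.6 are not visible, and a sentence in 7.6.1 breaks off. A handling rule there cannot be excluded. The dose rationale is also reduced, so any predicted human half-life is unseen.

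A reader might infer more than this supports:

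- That harm starts at a typical t1/2 of 20 h. At CV 20-30% it does not show above cohort sampling error there (Step 4).
- That AUC0-inf and CL/F are always biased. They are biased only as far as clearance varies.
- That the Part II washout would be too short. Protocol 4.3 and 5.1 require at least 5 half-lives if that exceeds one week, and nothing visible ties that figure to the filtered summary.

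**Conclusion.** The point holds as a conditional one. The 31.0 h individual cut-off follows directly from the 20% limit and the 72 h last sample under mono-exponential decline. The planned t1/2 summary is materially low from a typical t1/2 of about 24 h, by the amounts in Step 3.

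Those sizes assume near one-compartment kinetics, a measurable concentration at 72 h, no extended sampling, CV 20-30% and 10% noise. With two-phase profiles the onset is later and part of the t1/2 bias belongs to the slope fit. If the last measurable sample is earlier than 72 h, the cut-off falls (20.7 h for 48 h), but the direction of bias is then not uniform. If the human half-life proves short, the rule changes almost nothing. This is a cheap improvement to make before database lock. It is not a flaw that undermines the study.

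**What to change.** In SAP 7.5:

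- Let only R-squared above 80% and at least 3 terminal points decide whether t1/2 is reported. Reword the 3-point bullet, which now states a failure in a list of criteria to be met.
- Calculate t1/2, AUC0-inf, CL/F and Vz/F for those subjects, and flag the values when 20% or more of AUC is extrapolated.
- Print the number flagged per cohort.
- Present each summary both with and without the flagged values.

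The cost is SAP text and one extra table, with no added subjects, samples or visits. The statistical price is precision: in simulation the error SD of an individual t1/2 is about 11-16% for flagged subjects against 8-10% for unflagged at 10% noise, and 23-29% against 15-18% at 20% noise. With two-phase profiles the gain can be small. Where the terminal phase holds 60% of AUC and the fast phase has a 4-8 h half-life, the change recovers only 0.4-7 percentage points of t1/2 bias.

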### 4.3 Duration of Treatment

Part I: The study will be a SAD study with subjects admitting to the clinic on Day -1, and dosing on Day 1, followed by a residential period that concludes on Day 4 after assessments are completed, except in cases where the residence is extended due to safety concerns determined by the Investigator in consultation with the study Medical Monitor. An EOS visit will be performed 7 days after discharge from the in-patient unit (Day 11). The time from Screening to the EOS Visit is 39 days per cohort in Part I, inclusive of the Screening window.

Part II: The study will be a cross-over, single-dose study with 2 treatment periods. Admission will occur on Day -1, followed by dosing (Day 1), and a washout period of at least 1 week or at least 5 half-lives between dosing, whichever period is longer. The duration of the washout period could be adapted based on the review of PK data of INDV-2000. Subjects will be discharged on Day 2 unless tolerability from Part I indicates a longer stay is warranted. If that is the case, subjects will stay in the clinical unit until Day 4. If discharged on Day 2, subjects will return to the clinical unit on the morning of Day 3 and Day 4 for PK testing. Depending on PK results from Part I, the visit schedule may be modified. An EOS visit will be performed on Day 10 of the last Treatment Period (Part II, Period 2). The time from Screening to the EOS Visit is approximately 45 days, inclusive of the Screening window.

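### SAP 7.5 words one of its three terminal-slope criteria the wrong way round: read literally, every slope on 3 or more points is withheld

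*SAP*

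**What the plan says.** SAP 7.5 sets the rules for the non-compartmental analysis. Plasma parameters that need λz "will be presented as not calculated (NC), if at least one of the following criteria is not met". Three criteria follow:

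1. R² > 80%
2. "The terminal phase consists of less than 3 data points or"
3. %AUCextrap < 20%

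Just before this, the same section gives a separate rule for AUC: where "less than 3 consecutive measurable plasma concentrations are observed, the AUC parameters will not be estimated".

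SAP Table 3 shows which parameters need λz. AUC0-inf adds Clast/λz to AUC0-last. CL/F is dose divided by AUC0-inf. Vz/F uses both λz and AUC0-inf. The entry for t1/2 reads "Plasma terminal elimination half-life, calculated as" ln(2)/λz. Under "Plasma PK parameters of single doses of INDV-2000", Protocol 3.2 names AUC0-∞, CL/F and t1/2 among the secondary endpoints.

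SAP section 10 says that the preliminary PK at the cohort reviews follows SAP section 7, with nominal times replacing actual times. SAP section 11, which lists changes from the protocol's analyses, does not mention the λz criteria.

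**The concern.** The lead-in turns any unmet criterion into a not-calculated result, so each criterion has to describe an acceptable profile. The first and third do. The second describes an unacceptable one. A profile with a long, well-fitted terminal phase does not meet criterion 2 and is therefore withheld.

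This is an operative rule. It decides whether three secondary endpoints are reported for each subject, and it is reused during the trial. SAP section 9 presents the document as the a priori plan, so a programmer or quality checker should not have to override its text in order to apply it sensibly.

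**Working it through.** **Inputs.** The lead-in and three criteria come from SAP 7.5, the parameter definitions from SAP Table 3, and the last scheduled sample, "72 hr post-dose", from Protocol Appendix 4. The plan gives no figure to reproduce; the main point is one of logic.

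**Step 1: apply the rule as written.** A parameter is estimated only if all three criteria are met, that is R² > 80% and n < 3 and %AUCextrap < 20%, where n is the number of points in the terminal phase. The intended rule has n ≥ 3 in the middle. For n = 2, 3, 4 and 5, with R² and extrapolation each passing or failing, there are 4 × 2 × 2 = 16 combinations:

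| n | R² and extrapolation | As written | With n ≥ 3 |
|---|---|---|---|
| 2 | both pass | estimated | NC |
| 2 | either fails (3 combinations) | NC | NC |
| 3, 4 or 5 | both pass (3 combinations) | NC | estimated |
| 3, 4 or 5 | either fails (9 combinations) | NC | NC |

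As written, all 12 combinations with 3 or more points are NC. The only one estimated has 2 points, where R² equals 1 whatever the data, so the fit criterion checks nothing.

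**Step 2: try reversing the lead-in instead.** If parameters were NC when any criterion *is* met, criterion 2 would work. But then a good fit, or a small extrapolated area, would each be a reason to withhold. No single reading of the lead-in makes all three criteria sensible. Changing criterion 2 is the smallest repair.

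**Step 3: check the intended direction.** The AUC rule in the same section treats fewer than 3 measurable concentrations as a reason not to estimate. It is a different rule, about consecutive concentrations and not terminal-phase points, but it supports the reading that at least 3 points was meant.

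**Step 4: the optional matter of t1/2.** The 20% limit covers every λz parameter, including t1/2, which contains no AUC term. For mono-exponential decline (an assumption), the extrapolated share is exp(−ln2 × tlast / t1/2). Setting this to 0.20 gives

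t1/2 = tlast × ln2 / ln5 = 72 × 0.693 / 1.609 = 31.0 h.

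A noise-free one-compartment oral profile at the protocol's sampling times (absorption rate 1 per hour, assumed) agrees closely: 19.4% extrapolated at a half-life of 30 h and 20.5% at 31 h. With a last measurable sample at 72 h, the screen thus leaves out half-lives above about 31 h. At that limit the sampling window is ln5/ln2 = 2.32 half-lives.

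**The case against.** The strongest reply is that the error will not change any result. The literal rule would defeat the SAP's own reporting of t1/2, AUC0-inf and CL/F, so only one reading is workable, and it is probably the one that would be programmed. R², the number of points and λz itself go into the listings (SAP Table 3), so a misapplication would be visible. This stands, and it limits the severity. It does not remove the error, because the visible text nowhere states the right rule. Parts of SAP section 7 are absent from the public copy, so further text on NC values cannot be excluded.

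On t1/2, the reply is that one screen for all λz parameters contradicts nothing. Protocol 14.4.2 leaves PK detail to the SAP, and a half-life from fewer than about 2.3 half-lives of sampling is less precise. The perfect fit in the noise-free profile does not show that such slopes are reliable in real data. This also stands, so the t1/2 matter is a suggestion and not a fault.

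A reader might go further and infer that the 20% screen hides the need for a longer washout in Part II. Protocol 4.3 requires "a washout period of at least 1 week or at least 5 half-lives between dosing, whichever period is longer"; five half-lives exceed a week only above 168/5 = 33.6 h, and 31.0 h is lower. The documents do not support that inference, for three reasons:

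- It needs mono-exponential decline. If the terminal phase holds a share f of the AUC, the ceiling is 72 × ln2 / ln(f/0.20). This equals 33.6 h at f = 0.20 × 2^(72/33.6) = 0.88, and is higher for any smaller share.
- It needs sampling to stop at 72 h. Protocol 8.10.1 says that "up to 2 additional samples may be added or the schedule of samples may be modified". A last sample at 96 h, for illustration, raises the ceiling to 96 × ln2 / ln5 = 41.3 h.
- The protocol ties the washout to a review of PK data, not to the summarized t1/2. Listed λz values, the concentration profiles and a reduced N for t1/2 would all point to a long half-life.

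**Conclusion.** The wording error is certain and minor. As written, the rule withholds t1/2, AUC0-inf, AUC0-inf/D, CL/F and Vz/F for every slope on 3 or more points. Sensibly interpreted, it has no effect on results. This conclusion does not depend on what the half-life proves to be. Cmax, tmax, AUC0-last and the adverse-event primary endpoint are outside the rule.

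Two stronger conclusions should not be drawn. One is that the secondary PK endpoints will go unreported, which would require the rule to be programmed against its evident purpose. The other is that the reported t1/2 will be biased low by a stated amount. Protocol 1.4 says that human PK is not yet characterized, and the documents give neither a half-life nor its variability, so no size can be attached to this trial. The 31 h figure only marks where the screen begins to act, under mono-exponential decline and a last measurable sample at 72 h.

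**What to change.** Replace the three criteria in SAP 7.5 with one statement: parameters requiring λz are NC unless R² > 80%, the terminal phase has at least 3 data points, and %AUCextrap < 20%. In practice this rewords one bullet and tidies the lead-in. It needs no new data and should be in place before database lock; the interim PK should follow the same wording.

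Optional: apply the 20% limit only to AUC0-inf, AUC0-inf/D, CL/F and Vz/F, report t1/2 on R² and number of points, and flag t1/2 values with 20% or more extrapolation. The cost is one clause and one flag in the listing, and the flagged values would be less precise.
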